## 15. DATA HANDLING AND RECORD KEEPING

The investigator is responsible for ensuring the accuracy, completeness, legibility, and timeliness of the data reported.

Data collection forms will be derived from the eCRFs and provided by the SDCC to the sites to record and maintain data for each subject enrolled in the study. All source documents should be completed in a neat, legible manner to ensure accurate interpretation of data. Permanent ink is required to ensure clarity of reproduced copies. When making a change or correction, the original entry should be crossed out with a single line, and the change should be initialed and dated. Do not erase, overwrite, or use correction fluid or tape on the original.

Data reported in the eCRF should be consistent with the data collection form/source documents or the discrepancies should be documented.

The sponsor and/or its designee will provide guidance to investigators on making corrections to the data collection forms and eCRFs.

## 15.1. Data Management Responsibilities

All data collection forms and laboratory reports must be reviewed by the clinical team and data entry staff, who will ensure that they are accurate and complete. AEs must be graded, assessed for severity and causality, and reviewed by the site PI or designee. Data collection is the responsibility of the clinical trial staff at the site under the supervision of the site PI. During the study, the investigator must maintain complete and accurate documentation for the study.

The Emmes Corporation will serve as the SDCC for this study, and will be responsible for data management, quality review, analysis, and reporting of the study data.

# **15.2.** Data Capture Methods

Clinical data (including AEs, concomitant medications, and solicited events data) will be entered into a 21 CFR Part 11-compliant IDES provided by The Emmes Corporation. The data system includes password protection and internal quality checks, such as automatic range checks, to identify data that appear inconsistent, incomplete, or inaccurate. Clinical data will be entered directly from the data collection forms/source documents.

# 15.3. Types of Data

Data for this study will include safety, laboratory and outcome measures (e.g., solicited events, clinical cure, and therapeutic cure).

# 15.4. Timing/Reports

Safety data will be reviewed by the DSMB per the DSMB charter for this study. The DSMB will make a recommendation at that time as to the advisability of proceeding with further enrollment or use of study product. Interim statistical reports may be generated as deemed necessary and appropriate by DMID.

## 15.5. Study Records Retention

Records and documents pertaining to the conduct of this study, including data collection forms, source documents, consent forms, laboratory test results, and medication inventory records, must be retained by the investigator for at least 2 years following submission of a Biologics License Application or until DMID authorizes transfer or destruction of study records. No study records will be destroyed without prior authorization from NIAID.

#### 15.6. Protocol Deviations

A protocol deviation is any noncompliance with the clinical trial protocol, GCP, or MOP requirements. The noncompliance may be either on the part of the subject, the investigator, or the study site staff. As a result of deviations, corrective actions are to be developed by the site and implemented promptly.

These practices are consistent with ICH E6:

- 4.5 Compliance with Protocol, sections 4.5.1, 4.5.2, and 4.5.3
- 5.1 Quality Assurance and Quality Control, section 5.1.1
- 5.20 Noncompliance, sections 5.20.1, and 5.20.2.

It is the responsibility of the site to use continuous vigilance to identify and report deviations within 5 working days of identification of the protocol deviation, or within 5 working days of the scheduled protocol-required activity. All deviations must be promptly reported via The Emmes Corporation's IDES.

All protocol deviations, as defined above, must be addressed in study subject data collection forms. A completed copy of the DMID Protocol Deviation Form must be maintained in the Regulatory File, as well as in the subject's chart. Protocol deviations must be sent to the local IRB/IEC per their guidelines. The site principal investigator and personnel are responsible for knowing and adhering to their IRB requirements.

## 16. PUBLICATION POLICY

Following completion of the study, the investigator is expected to publish the results of this research in a scientific journal. The International Committee of Medical Journal Editors (ICMJE) member journals have adopted a trials-registration policy as a condition for publication. This policy requires that all clinical trials be registered in a public trials registry such as ClinicalTrials.gov, which is sponsored by the National Library of Medicine. Other biomedical journals are considering adopting similar policies. It is the responsibility of DMID to register this trial in an acceptable registry. Any clinical trial starting enrollment after 01 July 2005 must be registered on or before subject enrollment. For trials that began enrollment prior to this date, the ICMJE member journals will require registration by 13 September 2005, before considering the results of the trial for publication.

The ICMJE defines a clinical trial as any research project that prospectively assigns human subjects to intervention or comparison groups to study the cause-and-effect relationship between a medical intervention and a health outcome. Studies designed for other purposes, such as to study pharmacokinetics or major toxicity (e.g., Phase I trials), would be exempt from this policy.

## SUPPLEMENTS/APPENDICES

# **APPENDIX A: SCHEDULE OF EVENTS**

Table 5: **Schedule of Events** 

	T	T	T	tion	
	Visit 1	Visit 2	Visit 3	⊢ nin	5
	Day 1	8 (Window Days 8- 15)	28 (Window Days 22- 31)	Early Termination	Unscheduled
Informed Consent	X				
Inclusion/Exclusion	X				
Demographics	X				
Medical History 	X				
Concomitant Medication	X	X	X	X	X
Intercurrent Medical History 		X	X	X	X
Physical Exam	X				
Targeted Physical Exam		{X}	{X}	{X}	
Urine Pregnancy Test	X				
Gynecological Exam 	X	X	X	X	$\mathbf{X}^{\dagger}$
Vaginal Swabs for Nugent Score, bacterial/fungal cultures, trichomonas testing and appropriate samples for gonorrhea,	X	X	X	X	$X^{\dagger}$
chlamvdia testing 					
Vaginal Swab for Future Use (if subject consents to future use sample collection)	X	X	X	X	
Randomization	X				
Study Drug Administration	X				
Distribute Memory Aid and Study Drug Kit	X				
Counsel on intravaginal products, objects, sexual intercourse, and pregnancy avoidance	X	X			
Safety Labs	X	X	Χ^	X	
Telephone Contact to Stop Study Treatment	[X]				
Review Vaginal Symptomology	X	X	X	X	X
Review for insertion of intravaginal products, objects, and sexual intercourse		X	X	X	
Review Memory Aid and Collect Study Drug Kit		X	X +	X	
Assessment of Clinical Cure		X	X	X	
Assessment of Therapeutic Cure		X	X	X	
AE/SAE	X	X	X	X*	X

 <sup>1 Include menstrual, contraceptive, sexual history and history of previous episodes of vaginitis.
  Include use of intravaginal products or objects, sexual intercourse, treatment for vaginitis (other than the study product).
  Evaluate cervix, vagina, and vulva. Perform Vaginal pH, Saline Wet Mount, KOH Wet Mount, "Whiff Test".

-  Collect vaginal swabs for study specific tests (gram stain, cultures for bacterial flora and yeast) and trichomonas OSOM testing (if saline wet mount is negative, Visit 1 only) and institution specific samples for culture or molecular testing for *Chlamydia*, *Neisseria gonorrheae*. (Visit 1 only). Samples for gonorrhea and chlamydia testing will be consistent with standard of care at the institution).
-  Provide instructions on proper use of study drug applicator and observe first dose. Remaining 5 doses will be administered by the subject at home on Day 2 and Day 3.
-  Safety Laboratories Include: White blood cell count, hemoglobin, platelet count, absolute neutrophil count, creatinine, ALT, AST, total bilirubin, random glucose, HIV test (Visit 1 only).
- { } Targeted physical examination if indicated based on review of symptoms.
- [] Subjects will be called regarding grade 3 laboratory abnormalities within 24 hours of receipt of results and told to discontinue study product. Subjects with positive HIV, chlamydia or gonorrhea tests will be contacted as soon as possible after results are available and referred to their primary care provider for appropriate treatment.
- \*Memory Aid will be reviewed only if solicited events continued at Visit 2. Study Drug Kit returned only if not returned at Visit 2.
- \* If subject declines to return for an in-person visit, the study personnel will ask to contact the subject by telephone to assess for AE/SAEs on Day 22-31.
- † Evaluate cervix, vagina, and vulva. Collect appropriate clinical samples for genital infectious pathogens.
- \*\* Assess for vaginal discharge (quantity, color, odor, and consistency) and record presence or absence of objective signs of inflammation of cervix, vagina, and vulva (edema, erythema, excoriation).
- ^ Laboratory abnormalities that occurred between Visit 1 and Visit 2 or worsened at Visit 2 should be repeated until resolved or has stabilized. Further testing beyond Visit 3 is at the discretion of the PI or study investigator.

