
Visit 2 (Day 8 [Window Days 8-15]): At this visit, the study team will review the memory aid, the intercurrent medical history with assessment of AEs and SAEs, changes to the concomitant medications, a gynecological exam and a targeted physical exam based on symptoms will be performed, and vaginal pH and vaginal swabs for Gram stain, saline wet mount, KOH 10% wet mount and culture will be obtained. If signs and symptoms of vaginitis fail to resolve, the study clinician will refer the subjects to their clinician for standard treatment for BV or other etiologies of vaginitis at the clinician's discretion and the subject will be classified as a clinical failure at Visit 2 and/or 3. Follow-up hematology and chemistry labs (WBC count, hemoglobin, platelets, neutrophil count, creatinine, AST, ALT, total bilirubin, random glucose) for safety evaluation will be performed.

Visit 3 (Day 28 [Window Days 22-31]) will include a review of the intercurrent medical history, concomitant medications, AEs and SAEs, and a gynecological exam and a targeted physical exam based on symptoms. Vaginal pH and vaginal swabs for Gram stain, saline wet mount, KOH 10% wet mount and culture will be performed.

Subjects who have positive HIV, *Chlamydia*, or *Neisseria gonorrhoeae*, or a grade 3 laboratory results from Visit 1 will be contacted within 24 hours of receipt of laboratory results and will be asked to follow up with their provider. These subjects will be asked to discontinue the study therapy if the test result returns during the study product administration period of the study.

These subjects will continue in efficacy and safety follow up.

At visits 1, 2 and 3, an extra vaginal swab will be collected for future use, if subject consents to future use of specimens.

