#### 5.3.3. Reasons for Withdrawal

Any enrolled subject may withdraw or be withdrawn from the study for the following reasons:

- The subject withdraws consent
- The study is terminated
- For any reason that, in the opinion of the investigator, precludes the subject's participation in the study
- The subject no longer meets inclusion/exclusion criteria
- The subject develops an SAE that warrants withdrawal
- Other safety-related reasons at the discretion of the Principal Investigator (PI), DMID Medical Monitor, DSMB, or the subject

Any subject who has received at least one dose of study drug will be continued in efficacy and safety follow-up, if the subject agrees.

Subjects who test positive for chlamydia, gonorrhea, HIV, or are incidentally found to have a PAP result consistent with AGUS or HSIL, or have a Grade 3 laboratory abnormality will be discontinued from receiving study product if the result is available within the 3 days of study drug administration. They will be continued in follow up for safety and efficacy if they have received one dose of study drug. (PAP smears are not part of the study protocol, but may have been done outside of the study protocol by the subject's provider. Patient report of PAP smear abnormalities may be accepted as a criterion for discontinuation of study product).

If a subject develops a grade 3 laboratory abnormality while still receiving study product, they will be contacted and asked to discontinue study product and will be continued in safety and efficacy follow up. If any subject experiences a severe AE related to the study product, further doses will be discontinued. Additionally, subjects who experience a new or worsening solicited reactogenicity symptom that is grade 2 or higher will be asked to contact the study site to confirm the severity. A determination will be made whether to continue or discontinue the study product by a licensed study clinician. A subject who withdraws voluntarily from or has been discontinued from receiving further treatment will be encouraged to permit continued follow-up of AEs and to follow scheduled visits. If the subject agrees, study procedures (e.g., blood sampling for safety and vaginal sampling) may be continued.

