#### Administration

Study personnel will provide both verbal and written instructions for proper storage and administration. The first dose will be administered by the subject while the subject is still in clinic. The remaining 5 doses will be administered twice daily (morning and evening) with at least 8 hours between doses by the subject at home. If the subject received her first dose after 3 pm, she will be instructed to administer the next dose the following morning.

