## 11. STATISTICAL CONSIDERATIONS

#### 11.1. Introduction

This is a Phase 2, double-blind, randomized, placebo-controlled, multi-center trial comparing 5% Monolaurin Vaginal Gel to Vehicle Placebo Gel as outpatient therapy. A total of 120 eligible subjects with BV will be enrolled. Treatment assignments will be randomly allocated in a 2:1 ratio of test article to placebo, with the randomization stratified by clinical site. Each subject will receive intravaginal gel twice daily for three successive days for a total of 6 doses. There will be 3 clinic visits over 31 days.

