4. If answer to 'Inserted any intravaginal substances or objects other than the study treatment? ' is 'Yes', then concatenate answer to the substances that were inserted : Tampons, Spermicide, Douche, Diaphragm, Feminine deodorant product, Other: Other, specify. For example, if a subject marked Yes to Tampons, Douche and Other, where other specify is metronidazole gel, this column would be: Yes [Substances: Tampons, Douche, Other: metronidazole gel]. If answer is 'No' or 'Unknown', there will be no answer to substances.

				Subject Report		Clinic Assessment of Product Accountability		
Subject ID	Randomized Treatment Group	Actual Treatment Group	Number of Doses Taken as Scheduled	Number of Doses Taken Out of Window	Number of Doses Not Taken	Returned Used Applicators	Returned Unused Applicators	
XXXXXX	5% Monolaurin Vaginal Gel/Placebo Gel	5% Monolaurin Vaginal Gel/Placebo Gel	x	x	x	x	x	
xxxxxx	5% Monolaurin Vaginal Gel/Placebo Gel	5% Monolaurin Vaginal Gel/Placebo Gel	x	X	X	x	x	
XXXXXX	5% Monolaurin Vaginal Gel/Placebo Gel	5% Monolaurin Vaginal Gel/Placebo Gel	x	x	x	x	x	

Listing 9: 16.2.5 Compliance Data - Safety Population

1. Sort order is Subject ID.

2. Total number of doses is 6. Number of doses not taken will be calculated as 6 - Number of doses taken as scheduled - Number of doses taken out of window.

3. A dose will be considered 'Taken as Scheduled' on a given day if there are 2 doses taken on the same day at least 8 hours a part. The doses should be taken within 72 hours from first dose at least 8 hours apart and not more than 2 doses in a 24 hour period to be counted as all 6 being 'Taken as Scheduled''. If only one dose is taken on a day, then the first dose will be considered 'Taken as Scheduled'. If the first dose is taken after 3 pm, then only 1 dose will be taken on Day 1 and 1 dose on Day 4. Otherwise, a subject should have 2 doses taken on Day 1, 2 doses taken on Day 2 and 2 doses taken on Day 3. Any doses taken outside these time limits will be considered to be 'Taken Out of Window'.

4. If a subject does not have a record for 'Returned Used Applicators' or 'Returned Unused Applicators', then an 'Unknown' will be placed in those columns.

Subject ID	Randomized Treatment Group	Actual Treatment Group	Analysis Population	Visit Number	Study Day	Clinical Cure	Bacteriologic Cure	Therapeutic Cure
xxxxxxx	5% Monolaurin Vaginal Gel/Placebo Gel	5% Monolaurin Vaginal Gel/Placebo Gel	ITT, mITT, Evaluable, PP	xx	XX	Y/N	Y/N	Y/N

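### Footnote 5 of the Schedule of Events places five home doses on Days 2 and 3, where twice-daily dosing allows four; the stop rule is also worded with differing time windows

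*Protocol*

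**What the plan says.** The course is six doses: "Each subject will receive intravaginal gel twice daily for three successive days for a total of 6 doses" (protocol 11.1). The first is taken in the clinic. Three places then set out the other five.

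- Footnote 5 of the Schedule of Events, identical in protocol Table 5 and SAP Table 1: "Remaining 5 doses will be administered by the subject at home on Day 2 and Day 3".
- Protocol 6.2, Administration: "The remaining 5 doses will be administered twice daily (morning and evening) with at least 8 hours between doses by the subject at home". It adds: "If the subject received her first dose after 3 pm, she will be instructed to administer the next dose the following morning". Protocol 7.1 repeats the frequency and the 8-hour gap. Neither section counts doses by day.
- SAP Listing 9, implementation note 3, is the only place with a day-by-day layout. The ordinary case is two doses on each of Days 1, 2 and 3. Otherwise: "If the first dose is taken after 3 pm, then only 1 dose will be taken on Day 1 and 1 dose on Day 4".

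SAP 3.3.9 and 9.2 define compliance as at least 5 of 6 doses, taken inside 72 hours of the first, at least 8 hours apart, with a cap of two per 24 hours. Compliance is a condition of the Per-Protocol population (SAP 6.3.5).

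On stopping product after an adverse test result, protocol 5.3.3 (repeated in SAP 4.3) says such women "will be discontinued from receiving study product if the result is available within the 3 days of study drug administration". Protocol 4 says they are "asked to discontinue the study therapy if the test result returns during the study product administration period of the study". Protocol 6.3, the closing note of protocol 7.1, and SAP 9.2 give no day limit.

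**The concern.** The Schedule of Events is an operative instruction to sites. If its dosing footnote cannot be carried out at the stated frequency, a site has to depart from either the footnote or the dosing text. The SAP then scores what was taken against a third description. The statistical stake is Per-Protocol membership: a woman could follow one part of the documents and be classed as non-compliant by another.

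The stop-rule wording is a related but smaller matter. A woman who starts after 3 pm still has a dose on Day 4, so a stop window described in days may or may not reach that dose, depending on which section is read and how the days are counted.

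**Working it through.** **Dose count**

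1. Total course: 2 per day x 3 days = 6. This reproduces the six doses in protocol 11.1.
2. Footnote 5: capacity of Days 2 and 3 at twice daily is 2 x 2 = 4. The footnote needs 5, so it is over by 5 - 4 = 1, which is one of five home doses (20%) or one of the six-dose course (17%).
3. SAP Listing 9, first dose not after 3 pm: 2 + 2 + 2 = 6. The home doses fall 1 + 2 + 2 over Days 1-3.
4. SAP Listing 9, first dose after 3 pm: 1 + 2 + 2 + 1 = 6, with the middle days implied rather than stated. The home doses fall 2 + 2 + 1 over Days 2-4.
5. In neither layout do all five home doses fall on Days 2 and 3.

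Placing doses on a 30-minute grid, with first-dose times from 08:00 to 17:00, gave the same answer. Five doses fit on Days 2-3 only if the 8-hour gap is the sole constraint. With a cap of two per calendar day, or two per 24 hours, the maximum was four for every start time tried.

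**What the SAP does with a woman who follows the footnote**

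- *All five doses on Days 2 and 3.* Five doses on two dates put at least three on one date, and those three lie within 24 hours. That breaches the cap in SAP 3.3.9 and 9.2, so she is non-compliant and fails the Per-Protocol condition. Protocol 11.2 counts doses only, so there she would be compliant with 6 of 6. The exclusion comes from the timing limits in the SAP.
- *Twice daily on Days 2 and 3, then stop.* She takes 1 + 4 = 5 of 6. That meets the minimum exactly, and one further missed dose takes her below it.

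**Stop-rule versions**

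| Place | Triggers | Time limit |
|---|---|---|
| Protocol 5.3.3; SAP 4.3 | HIV, chlamydia, gonorrhea, Grade 3 laboratory value, AGUS/HSIL PAP | three days of administration |
| Protocol 4 | the same without PAP | the administration period |
| Protocol 6.3 and 7.1; SAP 9.2 | the same without PAP | none stated |
| Bracketed note to the Schedule of Events, both documents | Grade 3: told to stop. HIV, chlamydia, gonorrhea: contacted and referred, stopping not mentioned | none stated for stopping |

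For an after-3-pm starter, assume morning doses at 08:00. Dose 6 on Day 4 then comes 72 + 8 - s hours after a first dose at clock hour s. For s = 15.1 this is 64.9 h; for s = 17 it is 63 h. Dose 6 is outside calendar Days 1-3 but inside 72 hours. The three-day wording therefore misses it on the calendar reading and covers it on the hours reading.

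As an operative rule, the PAP trigger appears only with the three-day wording. The summary of changes in SAP 12 mentions it without a window.

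**The case against.** The best reply is that the footnote is a slip with little reach. Twice-daily dosing at least 8 hours apart is stated in protocol 6.2 and 7.1 and in SAP 4.4.1 and 9.2. Participants get verbal and written instructions, and the kits carry dosing instructions (protocol 6.1.2). A woman left with one unused applicator still meets the 5-of-6 threshold. The mITT population, on which the primary efficacy test rests, does not depend on compliance.

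Most of this stands and limits the consequence. It does not remove the contradiction. The footnote was carried unchanged into the SAP, which also holds the incompatible Listing 9 layout, and neither document says which text prevails.

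On stopping, a reader might infer that product is stopped only for results arriving in the first three days, so that every after-3-pm starter has an uncovered dose. The documents do not support that. Protocol 5.3.3 does not say that dosing may continue after a later result. Protocol 6.3 and 7.1 and SAP 9.2 state the stop without a day limit for HIV, chlamydia, gonorrhea and Grade 3 laboratory results. Three days read as 72 hours includes the Day 4 morning dose. Nor does protocol 4 supply a contrasting rule for PAP results, which it does not mention. What remains is that the wordings differ.

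**Conclusion.** The dosing calendars contradict each other by one dose, and this holds for any first-dose time. It needs no assumption beyond reading twice daily as two doses per day. Following footnote 5 with all five applicators makes a woman non-compliant under the SAP; following it at twice daily leaves her at the compliance minimum. The reach is Per-Protocol membership and the dose-timing displays. It is not the primary mITT comparison.

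The stop-rule point is secondary. It bites only if three days means calendar Days 1-3, and then only for a woman who started after 3 pm and whose result arrives after Day 3 but before dose 6. The documents do not give the share of such starters or the timing of results, so no count of affected women can be given. Nothing in the documents shows that any site dosed by the footnote.

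**What to change.** Reconcile footnote 5 in protocol Table 5 and SAP Table 1 with protocol 6.2 and SAP Listing 9, so that one calendar covers starts before and after 3 pm. Reconcile the stop-rule wording across protocol 4, 5.3.3, 6.3 and 7.1, the bracketed note to the Schedule of Events in both documents, and SAP 4.3 and 9.2, so that triggers and window agree everywhere. The sponsor decides which calendar and which window apply; this review proposes neither.

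The cost is wording changes in the two footnotes and the stop-rule passages, plus a memo to sites. No new data or participants are needed.
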